Protocol Study

Comparison of 3 direct laryngoscopes: Inscope DL blade size 3.5 and DL blade 3.5 Sun-Med GreenLine®/D™ to DL blade 3 SunMed GreenLine®/D™ for tracheal intubation in patients undergoing lumbar spine surgery, a prospective randomized study

11/06/2016

NCT02955511

Study Proposal

Comparison of 3 direct laryngoscopes: Inscope DL blade size 3.5 and DL blade 3.5 Sun-Med GreenLine®/D™ to DL blade 3 Sun-Med GreenLine®/D™ for tracheal intubation in patients undergoing lumbar spine surgery, a prospective randomized study

PRINCIPAL INVESTIGATOR

[name]., PhD., Program Director

CO-INVESTIGATORS

[name]
[name]
[name]
[name]
[name]
[name]

STUDY STAFF

INSTITUTION

Department of Anesthesiology
Cedars-Sinai Medical Center in Los Angeles
[name]
[name]

E-mail: [contact]

[contact]

[contact]

STUDY OBJECTIVES

Hypothesis

The use of Macintosh blade sized #3.5 (vs Macintosh size #3) would reduce the time required to achieve successful tracheal intubation and improve the glottic view.

Study objective

The purpose of this research study is to compare 3 different laryngoscope blades (sizes: 3.5, 3.5 and 3) and see if the blades size 3.5 will reduce the time required to achieve successful tracheal intubation and improve the physician's view of the glottis compared to the standard direct laryngoscope using the blade size 3, in patients undergoing lumbar surgery. The Sun-Med GreenLine®/D™ Macintosh Blade laryngoscope (size 3 and size 3.5) are already used at Cedars-Sinai Medical Center, but the Inscope Direct Laryngoscope (size 3.5) will be used at Cedars-Sinai Medical Center for the first time, as part of this research.

Primary end point: time to achieve successful tracheal intubation.

Secondary end points: glottic view at intubation, number of intubation attempts and effectiveness of the integrated suction in the Inscope Direct Laryngoscope.

BACKGROUND AND SIGNIFICANCE

Laryngoscopy is a common medical procedure used during elective and emergency intubations. The procedure is performed with either a direct or video laryngoscope with the device selected dependent on tool availability, provider (i.e. anesthesiologist, emergency physician, ENT physician, paramedic, etc.) preference, patient characteristics, and intubation difficulty. The direct laryngoscope technique involves a line-of-sight view from the patient's mouth to vocal cords along the blade of the scope. The direct laryngoscopy technique is the oldest technique associated with intubation. However, despite continuous improvements to direct laryngoscope size and shape since its inception in the late 19th century, no improvement yet addresses one major problem with airway visualization: the provider will experience a difficult intubation if liquids (i.e. gastric content, blood, mucus, etc.) obstruct the view.²

The Sun-Med GreenLine®/D™ Macintosh is a line of disposable direct Macintosh laryngoscopes. It features a stainless-steel blade and polycarbonate light-pipe to direct light into the airway. The handle, with integrated batteries and LED light, and blade are separately packaged prior to use. The GreenLine®/D™ Macintosh line is available in the standard sizes (0, 1, 2, 3, 4) and a new

size built to improve blade sizing for many adults 3.5 when a Mac 3 is too short, but a Mac 4 is too large. The GreenLine®/D™ Macintosh does not feature integrated suction.

The Inscope Direct Laryngoscope (developed by Inscope Medical Solutions) is a new disposable direct laryngoscope with two integrated and controllable (flow on/off) suction pathways. By integrating controllable suction with two independent pathways into the laryngoscope, the provider is able to select the primary (blade tip) suction pathway to clear secretions ahead of the laryngoscope and the secondary (at blade mid-length, below blade) to prevent and clear fluids that may re-accumulate during the procedure. Integrating the suction into the device prevents the common current practice of "juggling" the current suction catheter and endotracheal (breathing) tube in one hand while holding the patient's airway open with the other hand. While the incidence of aspiration of fluids into the lungs as a result of poor airway fluid management is low, the outcomes associated with this complication are very poor. ³⁻⁵

The Inscope Direct Laryngoscope has been developed as a Macintosh 3.5 sized blade to meet the size requirements of the majority of patients. This assumption is backed up by a trend among disposable direct laryngoscope manufacturers toward the 3.5 blade size, with at least 5 creating a 3.5 blade, including Teleflex, Sun-Med, Flexicare, Mercury Medical, and Curaplex.

In this study, we will compare the Inscope Direct Laryngoscope (blade size 3.5) with the currently used standard single-use Sun-Med Greenline/D Macintosh laryngoscopes DL-blade mac size and Sun-Med Greenline/D-blade size 3.5

All Direct Laryngoscopes are considered a Class I exempt device by the FDA. Because the risks associated with laryngoscopes are well known and documented, they are considered a non-significant risk device for studies involving humans.

STUDY DESIGN

This randomized, prospective study will analyze the efficacy of three different airway intubating devices. The three different devices are as follows:

- 1. DL-blade mac size 3 (Sun-Med GreenLine®/D™ Macintosh)
- 2. Inscope DL-blade size 3.5
- 3. DL-blade mac size 3.5 (Sun-Med Greenline®/D™ Macintosh)

The Investigator will record the patient's BMI, Mallampatti classification,^{6,7} size of mouth opening, thyro-mental distance, presence or absence of teeth, any unusual physical exam findings, time to successful intubation, number of unsuccessful attempts and the obtained glottic view. The necessity of rescue using a bougie, Mac #4, fiberoptic bronchoscope, LMA or videolaryngoscope. Also the end Tidal CO2 return, as well as the airway grade obtained by the anesthesiologist during intubation using the Cormack-Lehane classification^{8,9} and POGO score ¹⁰ in order to objectively assess and compare the two intubation techniques. Any other unusual events will be documented. All variables for all devices will be compared, evaluated and analyzed.

STUDY METHODS:

| Recruitment and Pre-operative period:

a) Study investigators will contact anesthesiologists to ask for any potential subjects who scheduled for surgery that day. As part of standard of care, the anesthesiologist will review and examine subject information and evaluate the subject's airway upon patient arrival to pre-op. If the attending anesthesiologist finds the subject match all inclusion criteria, they will introduce the patient to the study and provide the consent documents and patient letter. If the patient expresses interest, the attending anesthesiologist will contact the study team. A consenting investigator will then approach the patient to review the study and address any questions or concerns. If the patient would like to participate, consent will be obtained.

Only patients after the first case of the day will be approached for participation, giving second and third case patients time to review the study materials while they wait for their procedure. Patients are evaluated by the anesthesiologist upon arrival at pre-op.

Subjects will be approached prior to entering the pre-op stage and prior to having IV lines placed. Investigators will explain the study protocol including the potential benefits and potential risks. Patients will be told that they have the right to choose or refuse the study without any loss and any penalty because their participation in this study is voluntary.

- b) Only patients who have provided their written consent will be able to participate and undergo screening procedures for this study.
- c) Screening procedures will make sure patients meet all inclusion criteria. If patient meets all inclusion criteria, they will be accepted into the study.

Written informed consent will be collected from all subjects who meet the inclusion criteria and they will be randomly assigned to one of the 3 study groups according to a computer generated randomization number table.

The anesthesiologist conducting the intubation will be one of the preselected attending anesthesiologists who have extensive experience using all these intubation techniques. The subjects can discuss the study further with the investigators and ask many questions as they want and sign the consent form.

- (A) Before the case begins, each anesthesiologist will be informed which group the patient has been assigned to. The name of the assigned intubation device will be placed in sealed envelope and given to the participating anesthesiologist after they obtained informed consent and completed the patient's airway evaluation.
- (B) In order to help eliminate bias, the anesthesiologist's experience with each of the intubating devices in 10 or more patients will be verified.

Data of demographic information and physical exam performed (e.g., vital signs and airway evaluation) will be collected.

Il Operative period:

- (A) The randomly selected intubating device (blade) will be prepared and the endotracheal tube will be selected by the attending anesthesiologist.
- (B) The patient will be transported to the operating room and attached to all ASA standard monitors in the usual and customary fashion.
- (C) Standard monitoring devices: an automatic blood pressure cuff, three-lead electrocardiogram, capnograph, pulse oximeter, and an EEG bispectral (BIS) index monitor.
- (D) Midazolam 2mg will be giving as pre-medication.
- (E) The patient will be positioned on the OR table using a donut head pad to create an angle of approximately 30 degrees and bringing the chest up so the sternal notch is at the level of the external auditory meatus.
- (F) The patient will be pre-oxygenated 100% oxygen for 3 to 5 min prior to induction of anesthesia using a facemask to achieve a baseline O2 saturation greater than 98%.
- (G) A standardized induction technique (Standard of care induction) consisting of fentanyl 100 mcg IV, propofol 2 to 2.5 mg/kg IV, lidocaine 1 to 1.5 mg/kg IV, and succinylcholine 1 to 1.5 mg/kg IV. Supplemental bolus doses of propofol will be administered to increase the depth of anesthesia if necessary. If the anesthesiologists consider, additional doses

- of anesthetics will be administered to keep a BIS value < 60. Maintenance of the anesthesia with propofol infusion, cisatracurium, and other medications (and dosages) selected by the attending anesthesiologist.
- (H) The anesthesiologist will determine that the patient is adequately relaxed by verifying the patient has no twitches using a train-of-four nerve stimulator prior to laryngoscopy.
- (I) The investigator will begin timing as the anesthesiologist attending introduces the intubating device into the patient's mouth, obtains glottic view, intubates and End Tidal CO₂ returns.
- (J) The attending will let the study coordinator know the POGO (Percentage Of Glottic Opening) and the best glottic view grade obtained using the POGO grading system (0% to 100%), and the Cormack Lehane scoring system (1/2/3/4).
- (K) If the intubation attempt is unsuccessful, time will be stopped when the anesthesiologist removes the intubating device from the mouth.
- (L) Rescue with bougie, Mac #4, fiberoptic bronchoscope, LMA, videolaryngoscope or any device necessary used by the attending anesthesiologist will be recorded. Should the need for an adjunct airway device be necessary for ventilation, any device can be used in accordance with the American Society of Anesthesiologist (ASA) difficult airway algorithm in case of a difficult airway.
- (M) If the anesthesiologist uses the suction, its time and frequency will be recorded.
- (N) Vital signs (MAP, heart rate, end-tidal CO2 and SpO2) obtained at standardized intervals before, during and after tracheal intubation will be recorded.

III Post-operative period:

A postoperative follow-up assessment will be performed approximately 4 hours after surgery by a co-investigator blinded to the intubation device to evaluate:

- 1. The presence and severity of sore throat,
- 2. Any changes in voice (e.g., hoarseness),
- 3. Trauma to the lip,
- 4. Trauma to the tongue,
- 5. Trauma to the gum, or
- 6. Trauma to the teeth.

II. Data Analysis:

The total study size is estimated to be 120 patients. A sample size of 40 patients in each group is determined by power analysis based on:

The primary and secondary hypotheses, namely the mean time required to complete the intubation process, for each of 2 DL groups compared with the control (standard DL) group and with each other (i.e., Group 1 vs. Group 2, Group 1 vs. Group 3, Group 2 vs. Group 3). In a single factor ANOVA study, sample sizes of 40, 40, and 40 are obtained from the 3 groups whose means are to be compared. The total sample of 120 subjects achieves 88% power to detect a difference of at least 10 seconds using the Tukey-Kramer (Pairwise) multiple comparison test at a 0.05 significance level. The common standard deviation within a group is assumed to be 8.60.

The following items will be analyzed:

- 1. Demographic information (weight, height, BMI, age, gender)
- Airway evaluation: Mallampati class, mouth opening, presence or absence of teeth, gaps, thyro-mental distance, neck range of motion (Patients will be asked to move their neck in extension, flexion, rotation, and lateral binding)
- 3. Vital signs (MAP, heart rate, end-tidal CO2 and SpO2) obtained at standardized intervals before, during and after tracheal intubation
- 4. Type and amount of drugs administered during induction
- Assessment of the glottic view using the Cormack Lehane and POGO scoring systems at the time of tracheal intubation
- 6. Times from the passage of the blade between the teeth to obtain glottic view, to placement of the tracheal tube and the appearance of an end-tidal CO2 waveform
- 7. The number of intubation attempt(s) An intubation attempt was defined as the insertion of the laryngoscope blade in to the mouth of the patient, regardless of whether an attempt was made to insert a tracheal tube
- 8. The need to change to a different intubating device, and use of adjuvant airway device (eg, LMA, Bougie, fiberoptic bronchoscope, videolaryngoscope)
- 9. The use of suction and frequency
- 10. The presence and severity of trauma to the lip, tongue, gum, or teeth during intubation
- 11. The presence and severity of sore throat, any changes in voice, trauma to the lip, tongue, gum, or teeth in the recovery area
- 12. Blade Stained with Blood
- 13. Any complications

Definitions:

Intubation attempt: laryngoscope blade is inserted into the study participant. A failure will be recorded if the assigned laryngoscope is removed from the mouth to re-position twice.

Intubation Time: The time starts when the tip of laryngoscope blade passes the upper incisors and the time stops when the endotracheal tube is placed in the trachea, the cuff in inflate, and positive end-tidal CO2 detected.

Time to visualized vocal cords: The time starts when the tip of the video laryngoscope passes the upper incisors and the time stops when the provider has clearly visualized the vocal cords.

Ease of intubation: Immediately after the surgery, the performing anesthesiologist will be asked to judge the ease of intubation with each device on a scale from 1 to 4, where 1 = easy insertion without need of adjustment; 2 = need of one adjustment; 3 = two or more adjustments to obtain optimal visualization of the vocal cords, and 4 = impossible visualization and blind intubation or necessary use of an alternative airway device.

The provider will clear secretions as necessary to visualize and report the secretions encountered on a scale from 1 to 10, where 1 = no secretions and no visual obstruction 10=severe visual obstruction, unable to clear without removing device.

Postoperative evaluation: sore throat (0 = none and 10 = maximum discomfort), and whether they have postoperative dysphonia. Furthermore, the incidence of postoperative airway complications will be reported.

INCLUSION AND EXCLUSION CRITERIA

It is anticipated that approximately 120 patients age greater than 18 years scheduled to undergo lumbar spine surgery procedures will be enrolled in this study.

A. Inclusion Criteria

Subjects may be included in the study only if they meet all of the following criteria:

- 1) Patients scheduled to undergo lumbar spine surgery procedures under general anesthesia
- 2) Patients with a documented BMI of <35
- 3) Willingness and ability to sign an informed consent document
- 4) 18 80 years of age of either gender
- 5) ASA Class I– III adults

B. Exclusion Criteria

Subjects will be excluded from the study for any of the following reasons:

- 1) Patients who are deemed to be such a significant of an airway risk that they necessitate awake fiberoptic intubation or a difficult tracheal intubation is anticipated
- 2) Patients with history of difficult intubation
- 3) Patients with oxygen saturation less than 95% at room air
- 4) Patients with history facial abnormalities, oral-pharyngeal cancer or reconstructive surgery
- 5) Any pathologies of the mouth, pharynx or larynx, or the access to the airway is restricted
- 6) Patients with Immobilized cervical spine, or history of cervical abnormalities
- 7) Patients with a history of uncontrolled gastroesophageal reflux, hiatus hernia or diabetic gastroparesis
- 8) Any coagulation disorder
- 9) Pregnant patients
- 10) Emergency surgeries
- 11) Any other conditions or use of any medication which may interfere with the conduct of the Study

DATA HANDLING/RESOURCING: Physician Investigators will have access to the patients' medical records as part of this clinical study. All data will be recorded in forms provided by the Investigator(s). Collected data will be coded and used for research purposes only.

SUBJECT RECRUITMENT: Physician Investigators will interview and explain the details of the study to all potential subjects, who will subsequently be asked to sign an informed consent form to participate in this study.

Each participant will receive as compensation a \$50 gift card provided by the company Inscope.

POTENTIAL RISKS: The risks of this study are the same risks that the patient will undergo being induced and intubated for general anesthesia for the procedure. By participating in the study, the patient takes on no added risk relative to a patient who is not participating in the study. There will be no deviation from the customary and standard practices of general anesthesia for this study. The attending anesthesiologist is able to remove their patient from the study at any time should they deem some aspect to be unsafe for patient care. Independent of the randomization, in this study as in any standard intubation with direct laryngoscopy the subject during the intubation process has the risk of experience trauma to the lip, tongue, gum, or teeth, sore throat with any changes in voice.

Steps to be taken to minimize this research-related risk:

- Anesthesiologist is always the only one who decides whether or not the subject is candidate to be part of the study after a complete clinical evaluation of the airway in the pre-operative holding area.
- 2. Anesthesiologist is the only one preforming the intubation and each anesthesiologist participating in this study are experienced.
- In the case the anesthesiologist cannot perform the intubation procedure he/she is free to use any blade or airway intubating device they consider will be the best option for the subject.

MAINTAINANCE OF CONFIDENTIALITY: Patients' names will not be divulged and all data will be coded in the study records. Information gained during the course of the study will only be used by the investigators for the purpose of comparing the intubating devices. Copies of signed informed consent will be kept on file by the principal investigator, and no patient names or other identifying data will be used in any future publications. Any video or still images obtained of the patient's airway will not include any identifying features of the patient.

SPECIAL PRECAUTIONS: All the devices will be used by a board certified anesthesiologist who is, familiar with their use and trained to handle any untoward events.

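### The operator chooses the endotracheal tube after learning the assigned blade, and the tube is not recorded, so a tube choice that differs by arm could shift the primary intubation time

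*Protocol*

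**What the plan says.** **Order of events.** Protocol, Recruitment and Pre-operative period, item (A): "Before the case begins, each anesthesiologist will be informed which group the patient has been assigned to". The same item says that the device name, in a sealed envelope, is "given to the participating anesthesiologist after they obtained informed consent and completed the" airway evaluation. Only those two steps must come before the operator learns the blade.

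Protocol, Operative period, item (A), comes next: "The randomly selected intubating device (blade) will be prepared and the endotracheal tube will be selected by the attending anesthesiologist". Neither document gives a rule for tube size, type or shaping aid.

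**What is timed.** In the Definitions of both documents, Intubation Time starts when the blade tip passes the upper incisors. It stops when the tube is in the trachea, the cuff is inflated and end-tidal CO2 is detected.

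**What is recorded.** The Study Design section and the list of analysed items in both documents cover induction drugs (item 4), times by segment (item 6), attempts (item 7) and changes of device or adjuvant devices (item 8). The tube's size and type appear in none of them.

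**How it is analysed.** Data Analysis in both documents describes a single-factor ANOVA with Tukey-Kramer pairwise comparisons and names no covariate.

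**The concern.** The operator cannot be blinded with the blade in hand, but need not know the assignment when choosing the tube. As written, the operator does know it. Someone who expects a harder or less familiar intubation with one blade might choose a different tube, or shape it differently, for that arm. The protocol says that the Inscope device will be used at this centre for the first time, while both Sun-Med blades are already in use there, so different expectations are plausible.

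Tube passage lies inside the timed interval, so such a difference would enter the primary endpoint. The comparison would then estimate the blade together with whatever tube choice came with it, whereas the hypothesis is about blade size. A larger sample would not remove the shift. With no tube data, it could not be examined afterwards.

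**Working it through.** **1. Does the tube choice follow the assignment?** Yes. Pre-operative item (A) discloses the group after consent and airway evaluation. Operative item (A) then has the attending select the tube, in the same sentence as preparing the assigned blade.

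**2. Can the tube affect the primary time?** Yes. The clock starts at the incisors, so time spent preparing is not counted. It stops only after tube placement, cuff inflation and CO2 detection, so tube passage is counted.

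**3. Could a difference be seen?** In part. Item 6 splits the time from blade past the teeth to glottic view, to tube placement, to CO2 waveform. A tube effect would fall after the view is obtained. The blade can also affect that segment, so the split locates a difference without attributing it. Item 8 captures a bougie and similar devices, but not the tube.

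**4. How large could it be?** The documents give no figure, so this is illustration only. Assume a tube choice that saves 3 to 6 s is made in 50% of one arm and 20% of another:

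- (0.50 − 0.20) × 3 s = 0.9 s
- (0.50 − 0.20) × 6 s = 1.8 s
- As a share of the 10 s target: 9% to 18%

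**5. What would that do to the test?** Inputs from Data Analysis: SD 8.60 (taken as seconds), 40 per arm, alpha 0.05, Tukey-Kramer.

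- Degrees of freedom = 3 × 39 = 117
- Critical value = q(0.95; 3, 117)/√2 = 3.357/1.414 = 2.374
- SE of a pairwise difference = 8.60 × √(2/40) = 1.923 s

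The plan's own figure first. For a 10 s difference, 10/1.923 = 5.20, and the noncentral t distribution gives a per-pair power of 99.7%, not the stated 88%. A figure of 88% would need an SD of about 12.6. That discrepancy is a separate matter, but it is why both SDs are shown.

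Probability that a given pair is declared different when the blades do not differ, for an assumed shift in one arm:

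| Shift | SD 8.60 (SE 1.923) | SD 12.6 (SE 12.6 × √(2/40) = 2.817) |
|---|---|---|
| 0 s | 1.9% | 1.9% |
| 0.9 s | 3.3% | 2.5% |
| 1.8 s | 7.9% | 4.5% |
| 3 s | 21% | 9.9% |

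The last row would need, for example, a 10 s effect of tube choice with the same 30-point imbalance (0.30 × 10 = 3 s). Nothing in the documents supports or excludes it.

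**The case against.** **Other safeguards.** The attendings are preselected and experienced, and Pre-operative item (B) verifies use of each device in 10 or more patients, expressly to reduce bias. This weakens the argument from unfamiliarity. It sets a minimum, though, and does not equalise familiarity or remove expectation.

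**Tube choice as part of using the blade.** The hypothesis concerns the use of a size 3.5 blade, and a tube chosen in response to the blade could be seen as part of that use. This is a fair reading. But if tube choice is meant to be part of the comparison, it still has to be recorded for the result to be interpreted.

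**Induction and positioning.** A reader might infer that the whole of preparation is open to the same bias, since doses have ranges ("propofol 2 to 2.5 mg/kg IV, lidocaine 1 to 1.5 mg/kg IV, and succinylcholine 1 to 1.5 mg/kg IV") and "Supplemental bolus doses of propofol will be administered to increase the depth of anesthesia if necessary". The documents do not support carrying the point that far. Additional doses aim at a common target ("of anesthetics will be administered to keep a BIS value < 60"), relaxation is confirmed by "verifying the patient has no twitches using a train-of-four nerve stimulator prior to laryngoscopy", and induction drugs are recorded and analysed. One position is described for all arms ("using a donut head pad to create an angle of approximately 30 degrees"), and no person is named as choosing it.

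**Concealment.** A reader might also infer a failure of allocation concealment. The envelope is held until consent and airway evaluation are complete, so selection into the study is protected. The issue is conduct after allocation.

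**Invisibility.** Nor is a tube effect wholly invisible: items 6 and 8 give partial information. What stands is that they cannot separate tube from blade.

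**Conclusion.** The point holds for the tube and goes no further. The choice is made with the assignment known, under no stated rule, and without a record, and the tube's passage is part of the primary time. This is an avoidable route for performance bias.

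Its size and direction are unknown. The 0.9 to 1.8 s range rests wholly on the assumed 30-point imbalance and 3 to 6 s effect. On those assumptions it is small beside 10 s and raises a given pair's false-positive probability from 1.9% to between 3.3% and 7.9% at the plan's SD. A reader might infer that the primary result would be materially biased, or biased in favour of one blade. The documents give no basis for either. The case for changing the plan is that closing the gap costs very little.

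**What to change.** 1. **Protocol, Recruitment and Pre-operative period, item (A):** give the envelope only once consent, the airway evaluation and the operator's written choice of tube (size, type and any shaping aid) are all complete. Since the envelope already waits for the first two, this adds one condition. Align the item's opening sentence with it.
2. **Protocol, Operative period, item (A):** delete the clause on tube selection and keep the blade preparation.
3. **Recorded and analysed items, Protocol and SAP:** add tube size, type and shaping aid, and report them by arm. If the tube is changed after the envelope is opened, record the change and its reason.

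The operator keeps full discretion over the tube, and no clinical rule is set. Positioning, induction and the order of the other operative steps stay as they are. Opening the envelope only after positioning is not needed: it would re-order several operative steps and would still leave induction unblinded.

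The cost is one line on the data form and a slightly earlier tube decision. Sample size and power do not change.

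### Item (K) stops the clock when a failed blade is removed, but the plan does not connect that rule to the primary Intubation Time

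*Protocol*

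**What the plan says.** The protocol's Study objective section gives "Primary end point: time to achieve successful tracheal intubation". The Definitions in both protocol and SAP give Intubation Time one start, "The time starts when the tip of laryngoscope blade passes the upper incisors", and one stop, when the tube is in the trachea, the cuff is inflated and end-tidal CO2 is detected. Operative period item (I) agrees: timing covers the stretch in which the anesthesiologist "obtains glottic view, intubates and End Tidal CO₂ returns".

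Item (K) of the same section covers the other case: "If the intubation attempt is unsuccessful, time will be stopped when the anesthesiologist removes the intubating device from the mouth". Item 7 of the list of items analysed counts each insertion separately: "An intubation attempt was defined as the insertion of the laryngoscope blade in to the mouth of the patient". One patient can therefore have several attempts. The Definitions record a failure after two removals of the assigned blade for repositioning, and attach no time value to it.

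Failures are captured outside the primary time. The endpoints include "Secondary end points: glottic view at intubation, number of intubation attempts", and under item (L) rescue with "any device necessary used by the attending anesthesiologist will be recorded". On allocation, consented patients are told that "they will be randomly assigned to one of the 3 study groups according to a computer generated randomization number table". The protocol's Potential Risks section lets the anesthesiologist change device or remove a patient from the study. The Data Analysis section compares group mean times by single-factor ANOVA with Tukey-Kramer and names no analysis set.

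**The concern.** For a patient intubated at the first insertion, every rule in the plan gives the same time. For a patient who needs a second insertion they may not. The blade tip passes the incisors at each insertion, and (K) tells the timer to stop at removal. Nothing in the supplied text says whether the clock then restarts, whether attempt times are added, or whether the pause between attempts and any rescue time count.

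Two consequences follow if staff apply (K) as written. First, the pause is never recorded, so time from first insertion to success cannot be rebuilt afterwards. Second, a failed attempt may be entered as a time to removal, which can be no longer than a quick success. Both reduce the time charged to a blade that fails more often. The choice among readings could also be made after the data are seen.

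**Working it through.** **Plan figures used.** 40 patients per group, common SD 8.60 (taken as seconds), target difference 10 s, Tukey-Kramer at 0.05, stated power 88%. Check of that power: critical value 3.357/√2 = 2.374 on 117 df; noncentrality 10/(8.60 × √(2/40)) = 5.20; power for one pair 99.7%. The stated 88% does not reproduce. That is a separate matter and errs on the cautious side. The relevant baseline below is 99.7%.

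**Assumed inputs.** The documents give no failure rates or attempt durations. Assume a successful attempt takes 25 s, a failed attempt f = 30 s and the pause g = 30 s, and that the second attempt succeeds. Let p be first-pass success and d the difference in p between two arms.

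**One re-attempted patient under three readings.**
- One uninterrupted clock: 30 + 30 + 25 = 85 s.
- Summed attempts: 30 + 25 = 55 s.
- Stop at first removal: 30 s, close to the 25 s of a first-pass success.

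**Gap in mean time between arms.** The mean is 25p + (1 − p) × (value above), so the gap is:
- one clock: d(f + g)
- summed attempts: d·f
- stop at first removal: d(f − 25)

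| First-pass success | Expected failed first attempts per 40 | One clock | Summed | Stop at removal |
|---|---|---|---|---|
| 98% vs 95% (d = 0.03) | 0.8 vs 2 | 1.8 s | 0.9 s | 0.15 s |
| 95% vs 90% (d = 0.05) | 2 vs 4 | 3.0 s | 1.5 s | 0.25 s |

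Moving from one clock to summed attempts changes the gap by d·g = 0.9 or 1.5 s. Moving from one clock to stop at removal changes it by d(g + 25) = 1.65 or 2.75 s. Hence about 1 to 3 s.

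**Range.** With f and g each varied from 15 to 60 s:
- One-clock gap: 0.9 to 3.6 s (d = 0.03) and 1.5 to 6.0 s (d = 0.05).
- Change from one clock to summed: 0.45 to 1.8 s and 0.75 to 3.0 s.
- Change from one clock to stop at removal: 0.03 × (40 to 85) = 1.2 to 2.55 s, and 0.05 × (40 to 85) = 2.0 to 4.25 s.
- The stop-at-removal gap turns negative when f is below 25 s. At f = 15 s it is −0.3 or −0.5 s, so the blade that fails more often looks slightly faster.

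**Effect on the test.** Simulated trials of 3 × 40 used normal success times (mean 25 s, SD 8.6). Each re-attempt added 60 s (one clock) or 30 s (summed), with the same probability of a second re-attempt. With failures as the only difference between arms, Tukey-Kramer rejects for that pair in 4% (2% vs 5% re-attempts) and 6% (5% vs 10%) of trials on one clock, and in 3% and 5% on summed attempts. The reading shifts the estimate but seldom the test result.

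**Effect on power.** For a 10 s shift in one arm and the same re-attempt probability q in every arm, the variance is 8.6² + A²[q + 3q² − (q + q²)²], where A is the time added per re-attempt:

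| q | SD, one clock (A = 60) | Power | SD, summed (A = 30) | Power |
|---|---|---|---|---|
| 2% | 12 s | 89% | 9.6 s | 98% |
| 5% | 16 s | 65% | 11 s | 95% |
| 10% | 22 s | 38% | 13 s | 82% |

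Powers are simulated and good to a point or two.

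**The case against.** The strongest reply is that the endpoint is already defined. It is time to success, with one start and one stop, and (K) speaks of an attempt, which is one insertion. Read literally, a clock once started ends only at confirmed intubation, and a patient intubated at a later attempt has a value. This largely stands. A reader might infer that (K) contradicts the definition, or that the primary time is undefined. The documents support neither: the two rules can coexist, but nothing connects them. What survives is practical. Staff who obey (K) will not have the pause on record, whatever the analyst later intends.

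A second reply is that failures are not hidden, and this also stands. Attempts are a secondary endpoint, and device changes and rescue are recorded. They would not, however, correct a mean time that leaves out the time lost.

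Third, patients are randomised to groups, the means of those groups are compared, and failure is recorded against the assigned blade. Analysis by assignment is therefore the natural reading. Only the handling of removed patients and of those without a time is truly unstated.

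Fourth, one clock costs power and brings rescue-device time into a blade comparison. That is fair. The case for it is that it matches the stated endpoint and can be reduced to summed attempts later, whereas the reverse is impossible if the pause was not timed.

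**Conclusion.** The concern holds as a gap between a timing instruction and an endpoint definition. It should be fixed before data are collected, because an untimed pause cannot be recovered. Its likely size is modest: about 1 to 3 s in the difference of mean times for first-pass success differences of 3 to 5 points, against a 10 s target, with little effect on significance. This rests on assumed durations. Small numbers are plausible because anticipated and previous difficult intubation are excluded and the operators are experienced.

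A reader might infer a shift near the full 10 s target. The same formula gives 0.15 × 60 = 9 s for 95% vs 80% first-pass success, but nothing in the documents supports such a split. Nor does any text support counting the last attempt only. One part of the SAP was not available, so the conclusion applies to the text supplied.

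**What to change.** 1. Reconcile (K) with the definition: note the time of each blade insertion and removal while one clock keeps running, so that no interval is lost.
2. State in protocol and SAP, before data are seen, that primary Intubation Time runs from the first time the assigned blade passes the upper incisors to tube placed, cuff inflated and end-tidal CO2 detected. Report summed attempt times as a sensitivity analysis.
3. Analyse every randomised patient who has a time in the assigned group. Report by arm the assigned-blade failures and any patient without a time, including anyone in whom no tracheal tube was placed.

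ANOVA with Tukey-Kramer can stay, and clinical management is unchanged. The work is a few sentences and a few extra times on the record form. The real cost is power: a few long times raise the SD above 8.60. With re-attempts in 5% of patients, for example, power for a 10 s shift is about 65% on one clock against 95% on summed attempts. The team should accept that cost knowingly when it fixes the definition.
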